Main inclusion/exclusion criteria:	
Inclusion criteria
 
 1. Volunteers without clinical evidence of COVID-19 infection aged 18 years and older. 2. Participants who are at high risk of SARS-CoV-2 infection, defined as adults whose locations or circumstances put them at appreciable risk of exposure to SARS-CoV-2 and COVID-19. (see country specific addendum if needed to define further) 3. Must have a mobile phone and access to the Internet for data collection purposes. 4. Participants who are willing and able to provide informed consent via an electronic consent process. 
Exclusion criteria
 
 5. Weight outside range 50 kg – 120 kg (110 lbs – 265 lbs). 6. Self-reported or laboratory confirmed previous or current diagnosis of SARS-CoV-2. 7. Self-reported current acute respiratory infection. 8. Concurrent and/or recent use of the investigational product, a product considered to be equivalent to the investigational product, or any other product that is likely to interfere with the investigational products in this trial or the interpretation of trial data . 9. Self-reported known allergies to any of the IMPs and excipients of the IMPs and placebo. 10. Self-reported presence or history of the conditions listed in the appendices. 11. Self-reported current use of medication with known to interact with any of the medications listed in the appendices. 12. Inability or unwillingness to be followed up for the trial period.
Statistical methods and analysis:	The analysis of the primary endpoint will be by Bayesian logistic regression, adjusting for age as fixed effect, and sites as random effects. The secondary severity endpoint will be analyzed by Bayesian proportional odds model, with the same adjustment strategy. Interim analyses will be performed regularly for efficacy, futility and harm.

3 Background and Rationale

BACKGROUND

A. The Crisis of COVID-19

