Worldwide, non-pharmacological interventions like stay-at-home regulations, travel bans, and universal masking policies are used to reduce the reproductive number (R_0), but such measures relying on social distancing are not applicable to healthcare workers who have to be in close contact with people as part of their job. Whilst barrier interventions, namely personal protective equipment such as respirators, face protection, gowns and gloves are indicated as the minimum standard of prevention for healthcare workers who come into contact with SARS-CoV-2,^{8,9} these equipment measures are not

infallible and not always available. For other populations, barrier interventions such as face masks and personal screens are even less available. No pharmacological therapy been proven as effective for prevention or mitigation although remdesivir has been shown in some studies to reduce duration of ventilation and dexamethasone reduces mortality in severely ill patients. An ounce of mitigation is worth a pound of cure; this is especially true for highly virulent, pathogenic, and prevalent infectious diseases like SARS-CoV-2. Several specific vaccines for the SARS-CoV-2 have shown significant protective benefit, however several relevant caveats remain including:

- (i) it will take time to roll out a COVID-specific vaccine with an established safety profile to all at-risk populations;
- (ii) new strains of the virus might emerge for which the vaccine will not work.
- (iii) the vaccine might confer only brief immunity, since antibodies to SARS-CoV-2 often wane over a period of a few months.

We should therefore not simply rely on the development of a new vaccine and must also explore other pre-emptive and mitigation options. In order to have substantial positive impact, a pre-emptive therapy would have to either decrease the incidence of symptomatic COVID-19 or mitigate its average severity (duration of illness and complication rates).

[figure not shown]

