5.1 Overall design

Study Design

CROWN CORONATION is a large, Bayesian adaptive, pragmatic, participant-level randomized, multi-site, international placebo-controlled trial. Randomization will be stratified by age (<50 and ≥50), site and previous vaccination with a SARS-CoV-2 specific vaccine. Participants will be individuals at risk of contracting SARS-CoV-2. Participants will be randomized to education and surveillance plus Placebo or to a study arm with active interventions for a period of up to 60 days. The details can be found in the relevant appendices.

All participants will require a mobile phone to participate. This is standard in all the countries in this study. The participant, with help from the local trial team if required, will enrol online using the web-based eCRF system and record basic demographic and eligibility information.

The database will be hosted on UK-based servers which are expected to be managed by Sealed Envelope Ltd. Local investigators will have access to the part of the CRF to enable recording of adverse events, outcome data and/or severity of COVID-19 symptoms. Participants will be sent emails with a link to complete an initial participant health questionnaire and the regular data logs.

Participants will complete weekly SMS surveys. Participants who develop symptomatic COVID-19 during the last month of observation will at a minimum be followed-up until symptom resolution and at a maximum until 150 days (5 months) after randomization (whichever comes first).

The study flow overview is outlined in *Figure 3*. In the case of oral medications, the trial will provide adherence support interventions that have been shown in randomized controlled trials to improve adherence to Human Immunodeficiency Virus (HIV) treatment and adapted for HIV Pre-Exposure Prophylaxis (HIV PrEP) (e.g. two-way SMS with check in for those that report symptoms or adverse events).

[figure not shown]

Figure 3a: Detailed chart outlining the likely flow for each participant in the trial. This may be modified by individual centers.

[figure not shown]

Figure 3b: Flow Diagram showing mixed use of internet and tele-messaging through the course of the trial.

Sites

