8.2 Enrolment / Randomization Procedures

Participant registration will be undertaken online using computer or smartphone.

Following participant consent, and confirmation of eligibility (see section 8.1 for pre-treatment assessments) the registration and randomization procedure described below will be carried out.

Coordinated on-line registration and allocation of participant trial numbers will be required to enrol participants. Blocked randomization list will be used to allocate study participants to one of the groups, stratified by age, study location. The lists will be created by the study statistician based at the UCL CCTU and will be implemented through the online randomization portal, supplied by Sealed Envelope Ltd.

Participants will be assigned to treatment groups through consecutive allocation of subject numbers, and the use of a Trial Subject Enrolment Log which will be stored on the Sealed Envelope system. Participants will only be randomized to arms that they are eligible for (refer to section 7.1 and relevant appendix).

Participants are considered to be enrolled into the trial following: consent, pre-treatment assessments (see section 8.1) including confirmation of eligibility, completion of the registration/randomization process, allocation of the participant trial number and treatment by the central coordinating team/remote system.

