11.3 Randomization methods

Participant-level randomization will be used in the study.

The randomization sequence will be computer generated with permuted blocks. There will be initially equal numbers of participants (1:1) in each of the groups. Randomization will be stratified by age (<50 and ≥50) and site.

If the education and surveillance plus placebo arm is discontinued at an interim analysis, participants from this arm will be randomized to the remaining arms.

Modifications to the number of active treatment arms

Other arms can be added to CROWN CORONATION if evidence emerges that there are other suitable candidate prophylaxis options.

Participants will only be randomized to arms for which they are eligible. (e.g. pregnant women will not be randomized to the “vaccine vs placebo” arm).

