11.4.2 Primary outcome analysis

The threshold for declaring that an education and surveillance plus therapeutic agent(s) arm is superior to education and surveillance plus placebo will be based on the OR for the specific arm compared to education and surveillance plus placebo. The objective is to obtain sufficient certainty (95% at least) that $OR < 1$. In mathematical terms, this quantity is referred to as $P(OR < 1) > 95\%$.

Primary analysis models:

The primary endpoint of incidence of symptomatic laboratory-confirmed COVID-19 infection will be analysed using a Bayesian logistic regression, including as covariates the treatment arm, age (<50 vs. ≥50), and a random effect for site.

The prior distribution corresponding to the education and surveillance plus placebo arm will be such that it is centered on 15% for the event rate, midway between the 5%-25% range that we consider. The prior distribution corresponding to the OR of the treatment arm will be such that the OR is centered on 1. Further details on the prior distributions are provided in the SAP.

Additional multivariable analyses will be conducted, taking into account the following variables: sex, smoking, body mass index, HIV infection, pre-existing respiratory disease, diabetes (recent HbA1c), hypertension, and coronary artery disease.

Secondary outcomes:

The endpoint of severity of symptoms on the WHO scale will be analysed using a Bayesian proportional odds model, using the same adjustment approach as the primary endpoint.

Other secondary outcomes that are binary in nature will be analysed using Bayesian logistic regression, using the same adjustment methods as previously described.

In addition, time-to-event models will be used to assess the effect of the interventions on the time to incidence of symptomatic laboratory-confirmed COVID-19 infection over the 150-day period since receiving trial interventions.

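### Section 5.1 stratifies randomization by prior SARS-CoV-2 vaccination while Sections 8.2 and 11.3 do not; make them agree and, if vaccination stays, add it to the primary model

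*Combined protocol and SAP*

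**What the plan says.** The protocol describes the stratification three times, all in current text.

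| Section | Wording | Factors |
|---|---|---|
| 5.1 Overall design | "Randomization will be stratified by age (<50 and ≥50), site and previous vaccination with a SARS-CoV-2 specific vaccine" | age, site, vaccination |
| 8.2 Enrolment / Randomization Procedures | "stratified by age, study location" | age, site |
| 11.3 Randomization methods | "Randomization will be stratified by age (<50 and ≥50) and site" | age, site |

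The primary model in Section 11.4.2 is a Bayesian logistic regression "including as covariates the treatment arm, age (<50 vs. ≥50), and a random effect for site". The Summary agrees: "adjusting for age as fixed effect, and sites as random effects". The severity model is fitted "using the same adjustment approach as the primary endpoint", and the other binary secondary outcomes follow the same adjustment. SARS-CoV-2 vaccination is not among the eight additional covariates in Section 11.4.2 or the five subgroup factors in Section 11.4.3.

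The background (Section 3, part D) treats the factor as prognostic: "Several specific vaccines for the SARS-CoV-2 have shown significant protective benefit". Section 8.2 puts creation of the lists in the future. Section 11.4 describes itself as an overview and defers detail to a later SAP.

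**The concern.** The sections define different randomization lists. With age in two bands, Sections 8.2 and 11.3 give two strata per site. Section 5.1 gives four. A statistician who builds the list from one version departs from the other.

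There is a second, conditional consequence. The described model carries the other two stratifiers. If Section 5.1 is the intended version, the model leaves out a factor that the trial randomizes by and that the protocol regards as protective. The model standard error would then be somewhat too wide. The estimated OR would also not be conditional on vaccination, and Section 11.5 does not say what the OR compared with its 0.8 and 0.9 cut-offs is conditional on.

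**Working it through.** **Lists.** Strata per site are 2 (age) or 2 × 2 = 4 (age by vaccination). Section 5.1 prefers sites of at least 20 people. At 20, the average stratum holds 20/2 = 10 or 20/4 = 5.

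**Inputs from the plan.** OR 0.7, control rates of 5%, 10% and 15%, up to 2,500 per arm (Section 11.2.1); P(OR<1)>95% (Section 11.4.2); P(OR<0.8)>95% at the final analysis (Section 11.5).

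**Assumptions.** The vaccinated share q is 10-60%. Vaccination lowers the odds by 50-85% (odds ratio v = 0.5 to 0.15). Uptake is equal across sites, OR 0.7 is conditional on vaccination, and randomization is stratified by vaccination. Priors are flat with a normal approximation to the posterior; age and site are left out of the calculation.

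**Starting point.** With no vaccination effect and a 5% control rate, the treated rate is 3.553%. SE = √[1/(2500×0.05×0.95) + 1/(2500×0.03553×0.96447)] = 0.1417. Power = Φ(0.3567/0.1417 − 1.645) ≈ 0.808, consistent with the plan's figure of more than 80% at the top of its 2000-2500 range.

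**Formulas.** Let p0 and p1 be the control rates without and with vaccination, and t0 and t1 the treated rates.
- p0 solves (1−q)p0 + q·p1 = p, where p1 has odds v times those of p0. Each treated rate has 0.7 times the control odds. The overall treated rate is pT = (1−q)t0 + q·t1.
- OR without the term = [pT/(1−pT)] / [p/(1−p)].
- Model variance without the term = 1/[np(1−p)] + 1/[npT(1−pT)].
- Actual variance under stratification = sum over arms of [(1−q)a(1−a) + q·b(1−b)] / {n[m(1−m)]²}, with a and b the stratum rates and m the overall rate in that arm.
- Variance with the term = 1/(I0+I1), where each stratum's information is the inverse of the sum of its two arms' 1/[n·rate·(1−rate)].

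**Worked case: 15% control rate, 40% vaccinated, 85% lower odds.**
- p0 = 0.2226, p1 = 0.0412, t0 = 0.1669, t1 = 0.0292, pT = 0.1118.
- OR without the term: (0.1118/0.8882)/(0.15/0.85) = 0.7135.
- Model SE 0.0846, actual SE 0.0824, so 2.7% too wide. SE with the term: 0.0870.
- P(OR<1)>95%: 0.992 without, 0.993 with.
- P(OR<0.8)>95%: without, Φ[(−0.2231 + 0.3376 − 1.645×0.0846)/0.0824] = 0.382. With, Φ(0.1335/0.0870 − 1.645) = 0.456. The difference is 7.5 points.
- Correcting only the SE and keeping the OR at 0.7135 gives 0.399, or 1.7 of those points. The rest comes from moving the target from 0.7135 to 0.70. The adjusted SE is in fact the larger one, so this is not a gain in precision.

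**Range.** The first figure is for 10% vaccinated and 50% lower odds, the second for 60% and 85%.

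| Control rate | SE too wide by | OR without term | One-sided error at OR 1 | Loss, P(OR<1)>95% | Loss, P(OR<0.8)>95% |
|---|---|---|---|---|---|
| 5% | 0.1-1.5% | 0.700-0.708 | 0.050-0.047 | 0.0-0.7 points | 0.1-2.2 points |
| 10% | 0.1-3.1% | 0.701-0.715 | 0.050-0.044 | 0.0-0.5 | 0.2-6.7 |
| 15% | 0.2-4.7% | 0.701-0.723 | 0.050-0.041 | 0.0-0.2 | 0.4-12.4 |

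Uneven uptake shrinks the effect, because the site term absorbs part of it. In a simulation with a two-level site effect (40% vaccinated overall, 85% lower odds, control rate 16.9%), the P(OR<0.8) loss was 8.9 points with equal uptake. It was 7.6, 4.6 and 3.3 points with uptake of 20/60%, 5/75% and 0/80% in two halves of the sites.

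**The case against.** The strongest reply is that only the design overview in Section 5.1 is out of line. The two sections that describe the procedure agree with each other and with both statements of the model. If they are the intended version, nothing is missing from the analysis. If Section 5.1 is intended, the detailed SAP may still supply the term. Both points stand, so an omission from the final analysis cannot be shown. They do not remove the contradiction, since a later SAP cannot make three protocol sections agree.

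Few participants may be vaccinated, given the exclusion in Section 7.1.2 for products that interfere with the interventions or with interpretation. That would push the figures toward the low end of each range.

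A reader might infer three stronger things that the documents do not support.
- That the primary analysis is invalid or its error inflated. The one-sided error is at or below 0.05 throughout.
- That the trial loses substantial power. The larger losses concern P(OR<0.8), not the stated superiority rule. They depend on assumed uptake and vaccine effect, and arise mostly because 0.70 was assigned to the vaccination-conditional OR.
- That the placebo prior is undermined. The plan says "it is centered on 15% for the event rate". With 40% vaccinated and 85% lower odds, 15% overall corresponds to 22.3% in the unvaccinated, and 15% in the unvaccinated to 10.0% overall. No decision is shown to change, and the same reference-level question already exists for age.

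**Conclusion.** The inconsistency is real, and the documents do not settle which version is intended. Its certain consequence is two different randomization lists. The consequence for the model is conditional on Section 5.1 being intended and on the unsupplied SAP not adding the term.

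In that case the analysis is slightly conservative. Under the stated assumptions the SE is about 0-5% too wide, the OR moves from 0.70 to at most about 0.72, and power for P(OR<1)>95% falls by under 1 point. The chance of meeting P(OR<0.8)>95% falls by about 0.1-2 points at a 5% control rate, 0.2-7 at 10% and 0.4-12 at 15%. This is a matter of specification and worth correcting; it does not threaten the validity of the inference.

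**What to change.** Make Sections 5.1, 8.2 and 11.3 state the same factors and match the randomization list, preferably before it is generated. The documents do not show whether a list already exists; if one does, the text should match it.

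If vaccination is kept:
- Record status (yes/no) before randomization. The baseline items in Sections 5.1 and 8.1 do not name it, so confirm that the CRF does.
- Add it as a fixed effect, with its prior, to the primary model in the Summary and Section 11.4.2 and to the models that reuse that adjustment. Say in the same place which group the 15% placebo-rate prior describes.
- State in Section 11.5 that the OR compared with the thresholds is conditional on age, site and vaccination.

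If it is not kept, delete it from Section 5.1. The model then matches the design, and vaccination could still be used as an optional covariate if status is recorded before randomization.

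The cost is a few sentences and, if the factor stays, one covariate with its prior and thinner strata. At a 20-person site the average stratum would hold about 5 people instead of 10, so block size should be checked.

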6.1 Name and description of IMP(s)

Specific details regarding the IMP(s) used in each country is elaborated in the appendices. New dosage-based arm(s) or drugs might be added or removed following review and approval by relevant regulatory authorities. Each label for an IMP (active drug or placebo) will include the description of the study product and the information of the source (manufacturer/supplier, batch/lot number and expiry or best use by date).

Placebo will be aligned to the active IMP in terms of dosing schedule. The interventions will be continued for (up to) 60 days from enrolment; or until the participant is diagnosed with COVID-19; or development of a complication or safety concern or side effect necessitating stopping the intervention; or the intervention arm is stopped; or participants are no longer at risk of contact with SARS-CoV-2 infected patients (e.g. no longer new COVID-19 cases at the participating site). Treatment groups may be discontinued at interim analyses, and new treatment groups might be initiated. If a treatment group is discontinued due to perceived harm, participants in that group will be informed as soon as possible to stop taking the IMP.

6.2 Source of IMP(s), Manufacture, Distribution and Storage

The IMPs (see appendices) will be manufactured and QP released for use in the study by the holder of an MIA (IMP) license (or international equivalent). Sourcing of the IMP(s) is also discussed in the relevant site-specific IMP management plans.

6.3 Storage and handling of IMP(s) at site

All IMP aspects of the trial at participating sites are the responsibility of the site PI, who may delegate this duty to the local pharmacist or other appropriately trained personnel. The delegation of duties must be recorded on the Staff Signature and Delegation of Tasks log. Storage and handling (e.g., reconstitution, labeling) of the IMP will be completed in accordance with the relevant summary of product characteristics (SPC) and local IMP management plan. Treatment allocation will be sent to the pharmacist preparing the intervention at the point of randomization. The site pharmacist(s) will be unblinded to the treatment arm, they will dispense IMP(s) or placebo(s) in accordance with the treatment allocation and dosing regimen. Final presentation of the IMP or placebo will ensure participants are not aware of the treatment allocation. Detailed instructions are contained in the local IMP management plan.

6.4 Accountability of IMP(s)

IMP shipping arrangement instructions for sites will be described in each local IMP management plan. In each country, standardized procedures for monitoring of temperature and transport conditions of the IMP will apply and will be documented on the IMP shipping form in accordance with local requirements.

Upon receipt of the IMP, the site pharmacy will confirm receipt of the IMPs by emailing back the accompanying shipping form to the coordinating center and copies retained at the trial site's file. In cases where the IMP was damaged or not stored correctly this will warrant an urgent notification to the supplier and a replacement will be arranged. The supplier will be responsible for dispatching replacement IMPs to sites. Site pharmacy will be responsible for logging receipt of the IMPs on the site accountability log within the site pharmacy file. Site pharmacy will be responsible for storing the IMP in line with storage requirements as per the local IMP management plan. Site pharmacy will monitor temperature of IMP storage and report to the sponsor any temperature excursions that have occurred. Details of reporting temperature excursion are in the IMP management plan or country specific SOP for IMP Management. Full IMP accountability will be conducted during the trial. All IMP dispensed by pharmacy will be logged on the site accountability log within the site pharmacy file. In case of delay in drugs reaching the participants, it is important that the drug should have stability data supplied by the supplier to show that it is stable for at least 4 months and ideally longer than this.

IMP administration will be specific to the intervention and is detailed in the relevant appendix. Additionally, where relevant, participants will be reminded to adhere during the weekly SMS messaging. In vaccine arms, the IMP or placebo will be administered as a single dose by study personnel, making proper use of PPE.

All used/unused IMPs will be reconciled with site pharmacy, to be then updated in the IMP accountability log in the pharmacy site file. IMP destruction or disposal will be conducted, once authorized by the sponsor and in accordance with local practice, and this will be documented in the IMP destruction log in the site pharmacy file.

7 Selection of Participants

